Hypothesis 2a: Within the first three months after stroke, improvement in naming untrained pictures is negatively influenced by increased time to initiate treatment; but this effect of time is mitigated by taking SSRIs continuously from stroke onset because SSRIs can increase the window for neuroplasticity. To test this hypothesis, we will compare model 1 with model 2. Model 1 will be a linear regression of change in naming accuracy from baseline to 1 week post-treatment with the following regressor/predictor variables: treatment group (A-tDCS or sham), age, education, time from stroke onset to initiation of treatment (in days). Model 2 will include the regressors from models 1 and an indicator of SSRI use since baseline (yes= if patient had used SSRIs continuously from stroke onset, no=otherwise). We predict that in model 1, time from stroke onset to initiation of treatment (in days) will be negatively associated with the response variable. In model 2, we predict that time from stroke onset will no longer be associated with outcome; after adjusting for SSRI use (and all else in the model), the type III test for the effect of time from stroke onset will not be statistically significant and the magnitude of the parameter estimate will change by more than 10%.

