Communication through language is central to the human experience. Disorders of language, such as post stroke aphasia, impede interaction and hamper interpersonal connections and reintegration into family life, work, and school (Wise, 2003). In the setting of post stroke aphasia, some degree of language recovery over time is common, mostly occurring within the first few months after stroke; however, severe and debilitating language deficits frequently persist, and decline in cognitive/language abilities and overall function can occur in those who do not receive SALT(Dhamoon et al, 2012; Iadecola, 2013).

SALT is the mainstay of treatment for individuals with aphasia (Brady et al., 2012; Kurland et al., 2012). Clinicians strive to provide evidence-based interventions to improve language abilities after stroke. Meta-analyses indicate that about 100 hours of SALT are needed to significantly improve functional communication (Bhogal et al., 2003). Therapy is beneficial for language recovery in stroke, especially in the first three months post stroke (Hillis, 2010; Lazar et al., 2010); however, gains in therapy are variable and progress may be slow, especially in the chronic stage for patients with large lesions in the left hemisphere (Bhogal et al., 2003; Brady et al, 2012). Transcranial direct current stimulation (tDCS) is one method that has been proposed to boost behavioral language treatment in post stroke aphasia (Baker et al., 2010; Fiori et al., 2011; [name] et al., 2011; Jung et al., 2011; Marangolo et al., 2013; You et al., 2011). Although the precise mechanism of tDCS is still emerging (Weiss & Bikson, 2014), the prospect of augmenting the effectiveness of behavioral therapy is attractive to clinicians, patients, and their families and caregivers.

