It is plausible that SSRIs, which elevate synaptic serotonin, might enhance recovery by augmenting synaptic plasticity. Serotonin influences cortical reorganization (Gu & Singer, 1995; Jitsuki et al., 2011; Vetencourt et al., 2011) and adult neurogenesis in the hippocampus (Daszuta, 2011; Li et al., 2009) and may increase BDNF (Martinowich & Lu, 2007) (which may be a critical modulator of recovery implicated in the mechanism of tDCS as well. These mechanisms may account the positive effect of SSRIs (fluoxetine) on post-stroke motor recovery in humans (Chollet et al, 2011). In the cognitive domain, Jorge et al. (2010) reported that another SSRI (escitalopram) given in subacute stroke improved performance on the Repeatable Battery for the Assessment of Neuropsychological Status (RBANS), again independently of the effect on depression. Although there have been no randomized clinical trials, several small studies have shown positive effects of antidepressants on language outcomes (Kimura et al., 2000; Narushima et al., 2000; Tanaka, 2007) (but see Laska et al., 2005). Furthermore, there is high rate of post-stroke depression, ranging from 30 – 60% (Barker-Collo, 2007; Robinson et al., 1984) and post-stroke depression can be significantly reduced with pharmacotherapy (Hackett et al., 2008) Thus, there may be several positive effects of SSRIs after stroke; but the effects on mood and recovery appear to be independent (Chollet et al., 2011). We hypothesize that delay in initiation of A-tDCS/sham combined with SALT (within the first three months) will negatively impact the primary outcome measure (improvement in naming untrained stimuli post treatment), except in aphasic participants using SSRIs from stroke onset through post-treatment (Ng et al., 2015). However, SSRIs may enhance neuroplasticity, and augment effects of A-tDCS and/or effects of both SALT and A-tDCS in subacute stroke.

4. Study Procedures

- a. Study design, including the sequence and timing of study procedures (distinguish research procedures from those that are part of routine care).*

Study Procedures Overview

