Both groups will receive SALT, which is the current clinical standard of care for post-stroke aphasia. It is currently unknown whether or not tDCS augments the effect of SALT in the subacute phase after stroke. Therefore, a sham group is justified.

f. Definition of treatment failure or participant removal criteria

Participants will be removed from the study if they are unable to comply with task instructions or tolerate the tDCS procedure.

g. Description of what happens to participants receiving therapy when study ends or if a participant's participation in the study ends prematurely

When the study ends participants will continue to receive management with [name] or their own neurologist as usual (generally follow-up visits every about 6). If a patient's participation in the study ends prematurely s/he will still receive care as before. In sum, termination of the study or termination of participation in it will not affect regular therapy he or she may be receiving.

Changes to Procedures in the Event of a Pandemic

Upon resumption of our clinical research investigating the use of transcranial direct current stimulation (tDCS) in subacute stroke in the wake of the COVID-19 emergency, we will take several precautions to minimize the risk of exposure to COVID-19 for our participants as well as for members of our research team. We will rely on these same contingencies in the event of another pandemic.

- For face-to-face visits, we will primarily use the STAR Car, a mobile lab space (wheelchair accessible van) that would allow for isolated testing in lieu of testing in participants' homes or in our

Date: March 2, 2021

Principal Investigator: [name], MA

Application Number: IRB00089018

testing rooms located at the hospital, thus minimizing the risk of possible exposure to COVID-19. If the STAR Car cannot be used for a particular session, we will perform home visits (preferably outdoors, e.g. on a porch if privacy is not an issue) to limit contact of participants with others at the hospital setting.

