11. EXPLORATORY SUBGROUP ANALYSES

Exploratory analyses will also examine if any effects of A-tDCS vary across participants with different characteristics such as SSRI use, age (<55 vs. ≥55), education (<11 years completed vs. ≥12 years), time since stroke onset to initiation of treatment (<1 month vs. ≥1 month), and lesion volume. To address this, a regression of change in naming accuracy, which includes main effects and interaction terms with treatment group for these characteristics, will be used. Given the small sample size and since this is a secondary analysis, a significance level of 0.10 will be used to retain main effects or interaction with treatment in the final reported model. Finally, within the tDCS treatment group, we will compare mean change in naming untrained pictures for the fMRI versus the structural placement (CRF501 Q01) subgroups.

```

PROC MIXED;
  CLASS SUBJID ARM TYPE SUBGROUP;
  MODEL CHANGE=ARM | SUBGROUP WABAQ TYPE AGE;

  LSMEANS ARM*SUBGROUP/pdiff CL ALPHA=0.1;
RUN;

```

Hypothesis 2a: To test the hypothesis that within the first 3 months after stroke, improvement in naming untrained pictures is negatively influenced by increased time to initiate treatment; but this effect of time is mitigated by taking SSRIs continuously from stroke onset, we will carry out the secondary analysis as initially described above by comparing model 1 with model 2 as follows:

- Model 1 will be a linear regression of change in naming accuracy from baseline to 1 week post-treatment with the following regressor/predictor variables: treatment group (A-tDCS or sham), WABAQ, age, education, time from stroke onset to initiation of treatment (in days).
- Model 2 will include the regressors from models 1 and an indicator of SSRI use since baseline (yes= if patient had used SSRIs continuously from stroke onset, no=otherwise). We predict that in model 1, time from stroke onset to initiation of treatment (in days) will be negatively associated with the response variable. In model 2, we predict that time from stroke onset will no longer be associated with outcome; after adjusting for SSRI use (and all else in the model), the type III test for the effect of time from stroke onset will not be statistically significant and the magnitude of the parameter estimate will change by more than 10%.

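### The delay limb of Hypothesis 2a rests on a non-randomised days-from-stroke coefficient that spontaneous recovery alone can make negative

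*SAP*

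**What the plan says.** Hypothesis 2a has two limbs. The first is that "improvement in naming untrained pictures is negatively influenced by increased time to initiate treatment". The second is that continuous SSRI use since the stroke mitigates this. The end of the protocol's Background section puts the first limb as cause and effect: "delay in initiation of A-tDCS/sham combined with SALT (within the first three months) will negatively impact the primary outcome measure".

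The test compares two linear regressions of the change in naming from baseline to 1 week after treatment. In the SAP, Model 1 contains treatment group, WAB-R AQ, age, education and days from stroke onset to the start of treatment. The protocol version is the same without AQ. Model 2 adds an indicator of continuous SSRI use. Neither model has a treatment-by-days term.

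- Step 1: "We predict that in model 1, time from stroke onset to initiation of treatment (in days) will be negatively associated with the response variable".
- Step 2: in Model 2 the days effect is expected to be non-significant, and "the magnitude of the parameter estimate will change by more than 10" per cent.

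Three other statements bear on how step 1 can be read:

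- Protocol 4(e), on the sham group: "Both groups will receive SALT, which is the current clinical standard of care for post-stroke aphasia".
- Protocol section 3, Introduction: "some degree of language recovery over time is common, mostly occurring within the first few months after stroke".
- Protocol section 5: entry is limited to the first 3 months after stroke.

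Neither document names spontaneous recovery as another explanation for the Model 1 coefficient.

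**The concern.** The days coefficient compares people who happened to start early with people who happened to start late. It adds together three things: the slope of natural recovery, any effect of SALT timing and any effect of tDCS timing. No participant goes without SALT and nobody is randomised to a later start, so the first two cannot be separated by any covariate in the model. If recovery slows over the enrolment window, early starters gain more during the treatment period whether or not treatment works.

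The risk is that the expected course of the disease is reported as evidence that delaying treatment reduces the benefit. Early timing is part of the trial's rationale, so that reading would be attractive. The second limb also depends on the first. If the days coefficient is not an effect of treatment delay, there is no established delay effect for SSRIs to mitigate.

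**Working it through.** **1. The plan's own figure.** The only power statement concerns the primary comparison (SAP 8.3): 20 per arm, difference 23 (33 against 10), SD 22.2, two-sided alpha 0.05. The noncentrality is 23 / (22.2 × √(2/20)) = 23 / 7.02 = 3.28. With 38 df, the noncentral t gives 89.1%, which matches the stated 89%. No power or sample size is given for Hypothesis 2a. The SD of 22.2 and the planned sham change of 10 are used below.

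**2. What spontaneous recovery does to the coefficient.** Treatment lasts 3 weeks and the outcome is taken 1 week later, so the window is 21 + 7 = 28 days. Let R be the recoverable deficit at onset (items), τ the recovery time constant (days) and t the start day. With no treatment effect:

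gain(t) = R × e^(−t/τ) × (1 − e^(−28/τ))

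R, τ and the distribution of t are assumptions, because the documents give none of them. An example with R = 60 and τ = 30:

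- Start at day 14: 60 × 0.627 × 0.607 = 22.8 items.
- Start at day 80: 60 × 0.0695 × 0.607 = 2.5 items.

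The difference is 20.3 items with no treatment effect, close to the 23 items the trial is powered to detect between arms.

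**3. Are the assumed curves out of line with the plan?** With t uniform on days 7 to 90, the mean gain is R × (τ/83) × (e^(−7/τ) − e^(−90/τ)) × (1 − e^(−28/τ)).

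- R = 40, τ = 30: 40 × 0.268 × 0.607 = 6.5.
- R = 80, τ = 45: 80 × 0.391 × 0.463 = 14.5.

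These are the extremes for R = 40 to 80 and τ = 30 to 45, and they bracket the planned sham change of 10.

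**4. How often step 1 is met with no effect of SALT or tDCS.** Simulations used those R and τ values, 42 participants (the plan expects 40-45 completers), SD 22.2, and the SAP's Model 1. The rate counted is a negative days coefficient with two-sided p < 0.05, nominally 2.5% in that direction. The result depends on how much baseline AQ says about the deficit still present, and on the share of the deficit that can recover.

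| Assumption about AQ | Significantly negative |
|---|---|
| Tracks current deficit, share 1.0 | 3-5% |
| Tracks current deficit, share 0.7 | 7-24% |
| Tracks current deficit, share 0.4 | 10-51% |
| Carries no information | 16-68% |

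**5. A second set with a different calibration.** Here n was 40 to 50, start days were 5 to 90, τ was 20 to 45, total SD was 22.2, the share was 0.7, and the mean spontaneous gain was fixed at the planned sham value of 10. The SAP model was significantly negative in 9-38% of trials and the protocol model without AQ in 29-88%. With flat recovery the rate was 2%, so the excess comes from the recovery curve.

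**6. The complete two-step pattern, from the same second set.**

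- Step 1 significant, SSRI use independent of start time: about 0-1.5%.
- Step 1 significant, continuous SSRI use rarer in late starters (n = 45, τ = 30): 5% at mean gain 10 and 14% at mean gain 20.
- Step 1 needing only a negative sign, SSRI use independent, mean gain 10: roughly 3-30%. With flat recovery it was 24%, so this figure mainly reflects a loose rule.

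**7. The treatment-by-days term.** Recovery common to both arms largely cancels. With no treatment effect, the interaction was significant in about 4-8% of trials (nominal 5%). This leaves out runs with mean gain 20 and τ = 20, where the simulated gains varied more than the documented SD allows; there it was 10-15%.

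**The case against.** The strongest objection is that Hypothesis 2a is a conjunction. A reader might infer that spontaneous recovery alone can confirm the whole hypothesis, and the documents do not support that. Model 2 must also lose the days effect, and strong natural recovery tends to keep it there. When step 1 must be significant and SSRI use is unrelated to start time, the full pattern almost never appears. This stands, and it confines the point to the delay limb.

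Second, the SAP adjusts for AQ, measured just before treatment, and by its section 2 the SAP overrides the protocol. This also stands in part. The adjustment weakens the artefact, and nearly removes it if all of the deficit is recoverable and AQ follows it closely. Nothing in the documents supports assuming that. Equally, rates as high as two thirds should not be attributed to the SAP model, since they need an AQ that carries no information.

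Third, SAP section 11 already has a treatment-by-time subgroup test (under 1 month against 1 month or more), and the protocol's secondary analyses list time of initiation among the characteristics interacted with treatment. The 2a rule uses neither, so they do not change how its coefficient is read.

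Fourth, 2a concerns improvement under either treatment, so a treatment-by-days term answers a narrower question. That is correct, and the fix has to say so.

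Last, the analysis is exploratory, the step 1 prediction is worded as an association, and the decision on a Phase III trial rests on the primary comparison. This limits the consequence, but the hypothesis and the Background still state a causal effect of delay.

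**Conclusion.** The concern holds for the first limb of Hypothesis 2a. A negative days coefficient in Model 1 cannot show that delaying treatment reduces improvement, because slowing natural recovery predicts the same sign. This is a matter of identification and does not depend on the simulations.

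The size does depend on them. The central range is 7-24% against 2.5%, and it rests on assumed recovery curves, a uniform start-day distribution, a recoverable share of 0.7 and an AQ that follows current deficit. The other rows of the table show how far it moves.

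The evidence does not extend to the full SSRI pattern in general. That becomes more frequent only if SSRI use is related to start time or a negative sign alone is accepted. The primary test and its 89% power are untouched.

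**What to change.** In SAP section 11, Hypothesis 2a:

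1. Add treatment group by days from onset, with days continuous, to Models 1 and 2. Use that term, with its 95% CI, as the evidence on whether delay changes the effect of A-tDCS.
2. Report the days main effect as an association with time since stroke that includes spontaneous recovery, and drop the inference that it shows an effect of delaying treatment.
3. State that the timing effect of SALT, and any SSRI mitigation of it, cannot be identified without an arm that does not receive SALT.

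The cost is one model term and a few sentences, and SAP section 2 already provides for an update before database lock. The drawback is precision: with 40-50 participants the interaction will have a wide interval, and the result may be inconclusive.

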Hypothesis 2b: SSRI use since stroke onset is associated with greater gains with all treatments in the subacute period, independently of depression. To test this hypothesis, we will collapse aphasic participants across treatment groups, and compare the primary outcome measures for aphasic participants who have continuously taken SSRIs to aphasic participants who have not taken SSRIs. If SSRI use enhances plasticity at the subacute stage, it might augment the effect of A-tDCS and SALT without tDCS. Therefore, we predict that A-tDCS or sham combined with SALT over 15 sessions will be associated with greater gains in accuracy in naming untrained pictures in APHASIC PARTICIPANTS who have been taking SSRIs continuously since stroke onset, compared to the identical interventions in APHASIC PARTICIPANTS who have not been taking SSRIs. APHASIC PARTICIPANTS who have taken SSRIs for only part of the time will not be included in the analysis. Based on a recent survey of the inpatient stroke service, we predict about 50% of participants (n=20) will have taken SSRIs continuously, and almost 50% (n=17-20) will not have been exposed to SSRIs since stroke. The adjusted mean change (95% CI) in naming accuracy on untrained stimuli from baseline to 1 week, 5 weeks, and 20 weeks post-treatment for the SSRI-treated and the SSRI-untreated groups will be estimated using a mixed effects model adjusting for treatment group, baseline naming accuracy, time (with week 1, 5, or 20 as a categorical variable and a random effect for subject), and any subject characteristic found to be important in the secondary analysis (age, education, time of initiation of treatment, previous SALT and lesion volume, and interactions with treatment). We will then evaluate the independent effects of SSRI use, depression (measured at each time point with Patient Health Questionnaire-9, PHQ-9, Williams et al., 2005), and tDCS versus sham on the primary outcome variable using a multiple regression. Although we may not have the power to detect a significant effect of SSRIs, a few studies with similar small numbers have reported significant effects of SSRIs on stroke recovery measured with less sensitive measures such as the mRS. The goal of this exploratory aim is to determine whether or not we need to control for SSRI use in a subsequent clinical trial of A-tDCS in subacute stroke.

Date: March 2, 2021

Principal Investigator: [name], MA

Application Number: IRB00089018

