8.3 Sample Size Determination

If sample size in each group is 20, (a total sample size of 40), we will have 89% power to detect a difference in means of 23 (the difference between A-tDCS mean change in accuracy, μ_1 , of 33 and a sham mean change in accuracy, μ_2 , of 10) assuming that the standard deviation of change for both groups is 22.2 using a two group *t*-test with a two-sided alpha of 0.05. These mean changes for tDCS and sham and standard deviation of change are based on the one published sham-controlled study of tDCS combined with SALT in subacute stroke (You et al, 2011).

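### Hypothesis 2a's mitigation clause is not tested: Model 2 adds only an SSRI main effect, and the support rule checks for confounding rather than for a delay slope that differs by SSRI use.

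*SAP*

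**What the plan says.** SAP section 11 states 2a in two parts. Longer delay to treatment reduces improvement on untrained pictures, and "this effect of time is mitigated by taking SSRIs continuously from stroke onset". The protocol's Background (section 3) puts the second part more strongly: delay is expected to harm the outcome "except in aphasic participants using SSRIs from stroke onset through post-treatment".

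The test compares two linear regressions of change from baseline to 1 week. Model 1 contains arm, WAB AQ, age, education and days from stroke to treatment. Then: "Model 2 will include the regressors from models 1 and an indicator of SSRI use since baseline". The indicator is yes for continuous use from onset and no for everyone else.

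The predicted pattern has three parts:
- in Model 1, "time from stroke onset to initiation of treatment (in days) will be negatively associated with the response variable", with no significance level given;
- in Model 2, "the type III test for the effect of time from stroke onset will not be statistically significant";
- the days estimate changes by more than 10% between the models.

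Protocol section 2 sets out the same comparison without WAB AQ. The other regression in SAP section 11 is one "which includes main effects and interaction terms with treatment group for these characteristics". The remaining interactions in either document are with treatment or between visit and arm.

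**The concern.** To say that SSRIs mitigate the effect of delay, or remove it in users, is to say that the days slope differs between continuous users and others. Model 2 forces a single days slope on both groups, so it contains no parameter for that difference. The planned treatment interactions ask whether the tDCS effect varies with SSRI use or with delay, which is another question.

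A rule based on change in an estimate after adding a covariate detects confounding. The plan could therefore report that SSRIs protect against delay when users merely started sooner and did better, or miss real mitigation because adding the indicator leaves the common slope where it was. The stated goal of the SSRI work is to decide whether a later tDCS trial should control for SSRI use, so a misread result could carry forward.

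**Working it through.** **The plan's own figure.** The documents give no power for 2a. The primary calculation does reproduce: 20 per arm, difference 23, SD 22.2, two-sided 0.05, noncentral t with 38 df gives 89.1%, against 89% stated.

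**Inputs from the documents.** SSRI use about one half (protocol section 2, Hypothesis 2b: "we predict about 50% of participants (n=20) will have taken SSRIs continuously"); the SD (SAP 8.3: "assuming that the standard deviation of change for both groups is 22.2"); arm effect 23; n=40 (SAP 8.3) or 50 (SAP section 4).

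**Assumed.** Delay uniform on 5-90 days (mean 47.5, variance 85²/12 = 602.1); the slopes; the SSRI effect e; the latent correlation r between delay and SSRI use; no effect of WAB AQ, age or education. 22.2 is used as the residual SD unless stated.

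**1. Mitigation, SSRI use unrelated to delay.** Both models estimate the average slope. With -0.6 items/day in non-users and 0 in users: 0.5 × (-0.6) + 0.5 × 0 = -0.30 in Model 1 and -0.30 in Model 2. The expected change is 0%. This does not depend on the SD.

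**2. No mitigation, common slope -0.3, users start earlier and gain e items more.**
- Mean delay difference = 2 × 85 × arcsin(r/√2)/π = -15.5 days at r = -0.4.
- Slope of SSRI use on days = 0.25 × (-15.5)/602.1 = -0.0064 per day.
- Expected Model 1 coefficient = -0.3 - 0.0064e; expected Model 2 coefficient = -0.3.
- At e = 15: -0.3 - 0.096 = about -0.40 against -0.30, a change of 0.096/0.396 = 24%.
- The expected change passes 10% when e > 0.03/(0.9 × 0.0064) = about 5.2 items. At r = -0.2 (7.7 days earlier) the threshold is 0.03/(0.9 × 0.0032) = about 10.4 items.
- With e = 0 the expected shift is zero, whatever the timing difference.

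**3. How often the pattern appears at n=40**, requiring p<0.05 in Model 1. A range covers delay lines that meet at mean delay (lower) or at day 0 (higher).

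| Scenario | Pattern met |
|---|---|
| Full mitigation, r = 0 | 1-5% |
| No mitigation, SSRI +15, r = 0 | 3-4% |
| No mitigation, SSRI +15, r = -0.4 (users earlier) | about 22% |
| No mitigation, SSRI +15, r = +0.4 (users later) | under 1% |
| Full mitigation, r = -0.4 | 5-30% |

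The 30% in the last row has the same source as step 2. When the lines meet at day 0, users are ahead by 0.6 × 47.5 = 28.5 items at mean delay. That acts as a main effect: -0.30 - 0.0064 × 28.5 = -0.48 in Model 1 against -0.30 in Model 2.

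If Model 1 needs only a negative sign, the pattern is much more frequent. It is met in 15-43% under full mitigation at r = 0, about 51% with no mitigation at r = -0.4, and about 41% at r = +0.4.

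**4. The missing term.** A two-sided 0.05 test of SSRI × days is met in about 40-46% of trials under full mitigation at n=40 and in about 4-6% without mitigation.

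**The case against.** The aim is exploratory, SSRI use is not randomised, and no primary or safety conclusion rests on it. The frequencies depend on slopes, an SSRI effect and a correlation that the documents do not supply. The replacement is weak too: for a slope difference of 0.27 items/day, power is about 12-14% at n=40 and 14-17% at n=50. All of this stands. It limits the weight of the point and argues for an estimate rather than a test, but it does not make Model 2 estimate the hypothesised quantity.

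Stronger readings are tempting and go too far. A reader might infer that 2a is left wholly unanswered, but Model 1 addresses the delay clause directly. A reader might infer that any timing difference between SSRI users and others creates false support. In expectation it also needs users to gain more, and the direction matters: with users starting later, the stricter pattern almost disappears. Nor does the rule never fire under mitigation, as the last row of the table shows. Its fault is that it responds to the overlap of SSRI use, timing and average gain, not to a difference in slopes.

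**Conclusion.** The mitigation clause of 2a is not tested by the planned comparison in either document. This follows from the model and needs no simulation: Model 2 has one days slope, no SSRI-by-days term exists elsewhere, and with SSRI use unrelated to delay the expected coefficient does not move. The contrast of about 22% with 1-5% shows how the rule can mislead under particular assumed inputs; it does not forecast this trial. Confidence is high on the structure and limited on the percentages. The change should be made, but it concerns an exploratory aim only.

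**What to change.** Keep Model 1 for the delay clause. For the mitigation clause fit:

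change = arm + WAB AQ + age + education + days + SSRI + SSRI × days.

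Report the days slope in continuous SSRI users, the days slope in the comparison group, and their difference with a 95% CI, labelled exploratory and non-randomised. Stop treating non-significance plus a change of more than 10% as evidence of mitigation. If a p-value is shown, state its level, because the 0.10 in SAP 8.4 is for interactions with treatment.

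Define the comparison group. As coded it mixes partial users with never-users, so either call it not continuous users or exclude partial users, as Hypothesis 2b does.

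The cost is one product term and some rewording; both variables are already in Model 2, and SAP section 2 foresees an update before database lock. The drawback is imprecision. The 95% CI half-width for the slope difference is about 0.34-0.69 items/day at n=40 and 0.30-0.60 at n=50, depending on whether 22.2 is read as the residual or the total within-arm SD, where the lines meet, and r. Present it as an estimate, not a pass/fail result.
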